## **2. STUDY OBJECTIVES AND ENDPOINTS**

### **2.1. Objectives**

#### **2.1.1. Primary Objective**

The primary objective is to determine the proportion of patients with high-risk biochemically-recurrent (BCR) prostate cancer (PCa) that experiences decline or stabilization in PSA (without symptomatic/radiographic progression) after 12 weeks of nivolumab.

### **2.1.2. Secondary Objectives**

- Determine the maximal change (proportional) and best decline (absolute) in prostate specific antigen (PSA) during nivolumab treatment
- Describe the change in PSA doubling time (PSADT) during nivolumab therapy relative to baseline
- Determine the time to development of overt metastatic disease after treatment with nivolumab
- Determine the time to initiation of androgen deprivation therapy (ADT) after treatment with nivolumab
- Assess the toxicity of nivolumab monotherapy in patients with BCR PCa

### **2.1.3. Exploratory Objectives**

- Evaluate whether response to nivolumab treatment is enriched among patients with tumor programmed death-ligand 1 (PD-L1) expression on tumor cells and on tumor-infiltrating lymphocytes and antigen-presenting cells (APCs)
- Identify genomic biomarkers associated with response to nivolumab
- Evaluate correlations between alterations in DNA-damage-repair genes and PD-L1 expression
- Evaluate correlations between tumor-infiltrating lymphocytes and APCs with response to nivolumab
- Evaluate subtypes of “exhausted” tumor-infiltrating lymphocytes
- Explore whether peripheral T-cells are present that might recognize tumor neoantigens and whether these correlate with responses to nivolumab
- Assess for genomic alterations in circulating tumor DNA and correlate with mutations identified in primary tumor specimens
- Assess levels of plasma cytokines prior to initiation and during therapy and determine whether levels or changes in specific cytokines may be predictive biomarkers for response
- Assess PBMC subsets prior to initiation and during therapy and determine basal features or changes during therapy may be predictive biomarkers for response

## **2.2. Endpoints**

### **2.2.1. Primary Endpoint**

The primary endpoint is disease control, defined as PSA at 12 weeks less than 10% above baseline, or below baseline, and no symptomatic/radiographic progression, after 12 weeks of nivolumab treatment.

The expected increase in PSA at 12 weeks depends on doubling time. Based on the doubling time formula,  $\text{doubling time} = \log(2)/\log(1 + \text{growth rate})$ , a patient with a 10-month doubling time (the longest allowed under the exclusion criteria) would be expected to have an approximately 7.18% growth rate per month. PSA increase over 3 months (12 weeks) without intervention would be expected to be 23%. Faster doubling time would result in faster growth rate. Therefore, disease stability will be considered a PSA rise of less than 10% above baseline at 12 weeks. (This is in contrast with PCWG3, which considers PSA progression to be rise of at least 25% of baseline; as noted above, this criterion is too lenient in this setting given the expected PSA rise in the absence of intervention).

### **2.2.2. Secondary Endpoints**

- Maximal change in prostate specific antigen (PSA) during nivolumab treatment, as a percentage of baseline
- Best PSA response during nivolumab treatment, as an absolute change relative to baseline
- Change in PSA doubling time (PSADT) at end-of-study relative to baseline
- Time from enrollment to PSA progression (10% or greater increase in PSA relative to baseline)
- Time from enrollment to development of radiographic metastatic disease
- Time from enrollment to initiation of ADT
- Safety of nivolumab

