ENDPOINTS	
All subjects will be assessed for response to treatment using the recommendations of PCWG3.
 
Primary Endpoint:
 
 
• Disease control, defined as PSA at 12 weeks less than 10% above baseline, or below baseline, and no symptomatic/radiographic progression, after 12 weeks of nivolumab treatment
 
 
Secondary Endpoints:

[figure not shown]
	
 
• Maximal change in prostate specific antigen (PSA) during nivolumab treatment, as a percentage of baseline
 
• Best PSA response during nivolumab treatment, as an absolute change relative to baseline
 
• Change in PSA doubling time (PSADT) at end-of-study relative to baseline
 
• Time from enrollment to PSA progression (10% or greater increase in PSA relative to baseline)
 
• Time from enrollment to development of radiographic metastatic disease
 
• Time from enrollment to initiation of ADT
 
• Safety of nivolumab
 
 
Exploratory Endpoints:
 
 
• Correlation of tumor PD-L1 expression with response to nivolumab
 
• Correlation of tumor MSI-high status with response to nivolumab
 
• Correlation of tumor PD-L1 expression with tumor-infiltrating immune cells
 
• Exploration of exhausted tumor-infiltrating T-cell subsets
 
• Correlation of tumor genomic alterations with PD-L1 expression and nivolumab response, especially homologous recombination deficiencies (HRD; e.g. BRCA1, BRCA2, ATM, CHEK2), mismatch repair deficiencies (MMRd; e.g. MSH2 loss or alteration), status of tumor suppressors (e.g. PTEN and RB1), and ETS fusion status
 
• Detection of peripheral T-cells that recognize identified tumor neoantigens
 
• Detection of circulating tumor DNA and correlation of genomic alterations with those found in primary tumor
 
• Changes in soluble biomarkers during treatment
 

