## 6.7. Protocol Therapy Discontinuation

In addition to discontinuation from therapy related to toxicities as outlined above, a subject will also be discontinued from protocol therapy and followed per protocol under the following circumstances outlined below. The reason for discontinuation of protocol therapy will be documented on the electronic case report form (eCRF).

The Prostate Cancer Working Group 3 (PCWG3) recognizes that favorable effect of experimental therapies on PSA may be delayed for  $\geq 12$  weeks and recommends continuing treatment through early rises for a minimum of 12 weeks unless there is other evidence of progression.

PCWG3 recommends continuing experimental therapies for subjects who experience PSA rise after initial decline, in the absence of any radiographic or clinical progression. However, subjects in this trial do have access to a standard-of-care treatment in the form of ADT which can be used to delay development of metastatic disease, although a convincing survival benefit has not been established in this setting. This trial requires treatment discontinuation only for the reasons below, but investigators are advised to use discretion for patients with rapidly increasing PSAs (after 12 weeks of treatment). Patients believed to be clinically benefitting, for example based on decreased PSADT after starting nivolumab, could be continued on treatment at the investigator's discretion.

- Documented metastases on imaging (see Section 9 for definitions).
- Completed 2 years of treatment with nivolumab
- Site investigator determines a change of therapy (i.e. starting ADT) would be in the best interest of the subject
- Subject or legal representative (such as a parent or legal guardian) withdraws consent and requests to discontinue protocol therapy, whether due to unacceptable toxicity or for other reasons
  - In a subject decides to prematurely discontinue protocol therapy (“refuses treatment”), the subject should be asked if he or she may still be contacted for further

scheduled study assessments. The outcome of that discussion should be documented in both the medical records and in the eCRF.

- Unacceptable adverse experiences
- Intercurrent illness that prevents further administration of treatment
- Protocol therapy is interrupted for > 6 weeks (calculated from the date of the first missed dose). Any potential exceptions to this criteria must be discussed with and approved by the PI.

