## 9. CRITERIA FOR DISEASE EVALUATION

As per the Prostate Cancer Working Group 3 (PCWG3), a rising PSA is typically the first sign of tumor regrowth, followed later by worsening of disease by imaging and the development of clinical symptoms. Since there may be some interassay variability, subjects should have PSAs measured while on study at a single institution. PSAs from other institutions prior to enrollment are acceptable with the caveat that clear rise must be demonstrated and that interassay variability should be factored into this assessment. For this study, we are using the PCWG3-designated “control/relieve/eliminate” endpoints for therapies expected to be cytotoxic. In limited experience with MSI-high PCa that responds to PD-1 blockade, PSAs have fallen dramatically. It is also possible that stabilization of PSA will be a clinically meaningful endpoint if it delays or prevents development of metastatic disease and/or need for ADT; therefore, PSA stabilization is included in the primary endpoint.

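### Time to PSA progression counts the first unconfirmed 10% rise at any monthly draw, so a man with week-12 disease control can already be dated as progressed

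*Combined protocol and SAP*

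**What the plan says.** The Synopsis and section 2.2.2 define the endpoint as "Time from enrollment to PSA progression (10% or greater increase in PSA relative to baseline", and that is the whole definition. Section 9.1 defines PSA change, PSA doubling time (PSADT) and radiographic progression, but not PSA progression; the only confirmation rule there is for bone lesions. Section 12.2.2 adds a Kaplan-Meier summary. The study calendar in section 7 schedules PSA on day 1 of each 28-day cycle and at End of Study, and none in follow-up.

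The primary endpoint in section 2.2.1 is "disease control, defined as PSA at 12 weeks less than 10% above baseline, or below baseline", without symptomatic or radiographic progression. The PSA values at weeks 4 and 8 play no part in it. Section 2.2.1 derives the 10% cut-off from expected growth without treatment: a man with a 10-month doubling time "would be expected to have an approximately 7.18% growth rate per month", and "PSA increase over 3 months (12 weeks) without intervention would be expected to be 23" percent. It sets aside the PCWG3 threshold, "which considers PSA progression to be rise of at least 25% of baseline", as too lenient here.

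Section 6.7 notes that a favourable PSA effect may be delayed by 12 weeks or more and that PCWG3 "recommends continuing treatment through early rises for a minimum of 12 weeks unless there is other evidence of progression". On assay error, section 9 says "Since there may be some interassay variability, subjects should have PSAs measured while on study at a single institution"; no coefficient of variation (CV) is given.

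**The concern.** Read plainly, the event is the first scheduled PSA at or above 1.10 times baseline, whether at week 4, week 8 or later, and whether or not the next value falls back. Two groups of men are then misdated.

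The first is the delayed responder. His PSA keeps rising for a month or two and then comes down. He is a primary-endpoint success at week 12 and has a PSA progression dated before it.

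The second is the man whose PSA is truly stable. He is compared with his own single baseline value at every draw, so measurement error gives him repeated chances of crossing +10%.

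In both cases the primary and secondary results contradict each other for the same man. With 20 and 14 men per cohort, a few misdated events visibly move a Kaplan-Meier curve.

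**Working it through.** **Step 1: reproduce the plan's growth figures.** At a PSADT of 10 months the monthly growth is 2^(1/10) − 1 = 7.18%. Over 3 months it is 1.0718³ − 1 = 23.1%. Both match section 2.2.1. Exactly 84 days is 84/30.44 = 2.76 months and gives 21.1%.

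**Step 2: when does untreated PSA cross +10%?** Time to +10% = PSADT × ln(1.1)/ln(2) = 0.1375 × PSADT. Rise at time t = 2^(t/PSADT) − 1.

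| PSADT | Time to +10% | Rise at week 4 | Rise at week 8 |
|---|---|---|---|
| 3 months | 0.41 months (13 days) | 23.7% | 53.0% |
| 6 months | 0.83 months (25 days) | 11.2% | 23.7% |
| 10 months | 1.38 months (42 days) | 6.6% | 13.6% |

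The doubling time that just reaches +10% at week 4 (0.92 months) is 0.92/0.1375 = 6.7 months. For week 8 (1.84 months) it is 13.4 months, beyond the eligibility limit of 10. So an unaffected PSA crosses by week 4 in men with a PSADT under 6.7 months, and by week 8 in every eligible man. If the drug acts only after that and brings PSA below 1.10 times baseline at week 12, the man is both progressed and controlled. This step needs no assumption about measurement error.

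**Step 3: noise in truly flat men.** Assumptions: constant true PSA, a single noisy baseline, draws at weeks 4, 8 and 12, independent log-normal error, and 400,000 simulated men per CV. The CV is an assumption and is therefore shown as a range. An event is an observed PSA ≥ 1.10 times the observed baseline; confirmed means two consecutive draws at or above the cut-off.

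| Assumed CV | Unconfirmed event by week 12 | Confirmed within week 12 | Event at week 4 or 8 among men controlled at week 12 | Same, if confirmed |
|---|---|---|---|---|
| 3% | 3% | 0.3% | 2% | 0.1% |
| 5% | 20% | 4% | 12% | 2% |
| 10% | 46% | 17% | 28% | 6% |
| 15% | 56% | 24% | 35% | 9% |

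If a week-12 rise may also be confirmed at week 16, the confirmed column becomes 0.4, 6, 21 and 30%.

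**Step 4: how much of the whole curve is noise?** Mix 25% flat men (the design alternative for the PD-L1-positive cohort in section 12.1) with 75% rising men whose PSADT is uniform on 3 to 10 months (assumed). Flat men supply about 1, 6, 14 and 17% of the events by week 12 at CVs of 3, 5, 10 and 15%. With 50% flat men the share is 3 to 38%.

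**Step 5: the design figures.** Exact binomial, 20 men, success at 2 or more: alpha 0.017 at 1%, power 97.6% at 25%. For 14 men, success at 1 or more: alpha 0.131, power 95.6% at 20%. These match section 12.1, and none depends on time to PSA progression.

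**The case against.** Several objections have force.

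- **Whole curve.** A reader might infer that the Kaplan-Meier curve would mostly show assay noise. Step 4 does not support that: most men are expected to be rising, and most early events would be real growth. The noise problem belongs to the stable subgroup.
- **Size of the CV.** The documents give none, and single-institution testing limits it. At 3% the noise effect is small. Section 1.1 considers assay variation only as a possible source of false stability, so it does not answer the question of false progression.
- **The 10% threshold.** Its rationale, growth without treatment, also supports a cut-off below 25% for progression. What is missing is confirmation and the handling of early rises.
- **PCWG3.** The Synopsis says "All subjects will be assessed for response to treatment using the recommendations of PCWG3". A reader might infer that this supplies a confirmation rule, or that the endpoint violates one. It is a general statement about response, and section 6.7 concerns continuing treatment, not dating progression. Section 6.7 is relevant only because it accepts that effects can be late.
- **Reference value.** A reader might infer that measuring from baseline is an error because responders are called late. After a 50% decline with regrowth at a PSADT of 6 months, reaching 1.10 times baseline takes 6 × log2(1.1/0.5) = 6.8 months from nadir. But time until PSA exceeds its starting level is a coherent quantity with the same reference as the primary endpoint. After a 10% decline, the baseline reference adds only PSADT × log2(1/0.9) = 0.5 to 1.5 months at PSADT 3 to 10 months. Measuring from nadir is a preference.

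What stands is the conflict with week-12 disease control and the avoidable false events in stable men.

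**Conclusion.** The point holds in a limited form. Followed literally, the definition can date a man as progressed at week 4 or 8 while the primary endpoint counts him as controlled at week 12. For delayed responders this follows from the protocol's own formula and its own statement about late effects. For stable men the size depends on an assumed CV: 3 to 56% have an unconfirmed event by week 12 across CVs of 3 to 15%, against 0.3 to 24% with confirmation. That the rule is unconfirmed and applies at any visit is read from the absence of any other rule.

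The stakes are small. This is one descriptive secondary endpoint with no test attached, and section 6.7 lists no PSA threshold that requires treatment to stop. Alpha, power, sample size and the success rule are untouched. Severity: minor; a cheap improvement.

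**What to change.** Change the analysis definition only; no treatment decision is affected. Define PSA progression as a rise of at least 10% above baseline, confirmed by the next scheduled PSA and dated at the first rise. Do not count a rise before week 12 if the week-12 PSA is below the cut-off. By construction, a man whose week-12 PSA meets the disease-control cut-off then cannot have an earlier PSA progression date.

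The cost is a few lines in sections 2.2.2, 9.1 and 12.2.2 and the matching Synopsis entry; the monthly PSAs are already drawn. The downside is that a rise at the last draw before a man goes off drug cannot be confirmed, since no PSA is scheduled in follow-up. The text should say whether such a rise is flagged or censored, and how an early rise is handled when there is no week-12 PSA.

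Time from nadir to a confirmed rise, in men whose PSA declined, may be added as an optional supplementary summary.

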### **2.2.3. Exploratory Endpoints**

- Correlation of tumor PD-L1 expression with response to nivolumab
- Correlation of tumor MSI-high status with response to nivolumab
- Correlation of tumor PD-L1 expression with tumor-infiltrating immune cells
- Exploration of exhausted tumor-infiltrating T-cell subsets
- Correlation of tumor genomic alterations with PD-L1 expression and nivolumab response, especially homologous recombination deficiencies (HRD; e.g. BRCA1, BRCA2, ATM, CHEK2), mismatch repair deficiencies (MMRd; e.g. MSH2 loss or alteration), status of tumor suppressors (e.g. PTEN and RB1), and ETS fusion status
- Detection of peripheral T-cells that recognize identified tumor neoantigens
- Detection of circulating tumor DNA and correlation of genomic alterations with those found in primary tumor
- Changes in soluble biomarkers during treatment

## **3. ELIGIBILITY CRITERIA**

### **3.1. Inclusion Criteria**

Eligible subjects must meet all of the following inclusion criteria:

1. Patients must have signed an informed-consent form indicating that the patient understands the purpose of and procedures required for the study and is willing to participate in the study.
2. Patients must have a history of prostate adenocarcinoma (adenocarcinoma must be the primary histology; secondary components of variant histologies are acceptable) confirmed on biopsy and treated with primary radical prostatectomy (RP) or definitive radiation (RT). Prior salvage RT is acceptable.
3. Patients must have experienced biochemical recurrence (BCR) with most recent PSA  $\geq 0.5$  ng/mL. For patients who received primary RT, PSA must have risen to  $\geq 2$  ng/mL above the nadir (per RTOG-ASTRO consensus criteria).
  - a. No evidence of metastases on conventional imaging. (See Section 9 for definitions of radiographic metastases. As per PCWG3, lymph nodes  $\geq 1.5$  cm are considered pathologic and nodes  $1.0 < 1.5$  cm may be considered pathologic but with clinical discretion. Metastases seen on fluciclovine PET, NaFl, or PSMA scans or other advanced imaging but not on conventional imaging are acceptable. Advanced imaging such as fluciclovine PET or PSMA PET with no evidence of metastases may replace conventional imaging for eligibility. NaFl scan would only replace bone scan.)
4. PSA doubling time (PSADT)  $< 10$  months
  - a. PSADT: calculated as per PCWG3 and the Memorial Sloan Kettering Cancer Center calculator:  
[https://www.mskcc.org/nomograms/prostate/psa\\_doubling\\_time](https://www.mskcc.org/nomograms/prostate/psa_doubling_time)  
 With linear regression model of normal logarithm of PSA and time, based on:
    - i. At least 3 consecutive PSA values with each value  $\geq 0.2$  ng/mL
    - ii. Interval between first and last PSA values is  $\geq 8$  weeks but  $\leq 12$  months
5. Archival tissue is mandatory, either prostatectomy specimen or (in patients who received primary RT) diagnostic core biopsies. Patients must consent to next-generation sequencing performed on this tissue.
  - a. If diagnostic core biopsies are only available tissue, at least 3 cores must be involved by tumor
6. ECOG performance status 0-1
7. Age  $\geq 18$  years
8. Adequate organ and marrow function:

System	Laboratory Value
Hematological	
White blood cell (WBC)	$\geq 2000/\mu\text{L}$
Absolute Neutrophil Count (ANC)	$\geq 1500/\mu\text{L}$
Platelets (Plt)	$\geq 100 \times 10^3/\mu\text{L}$
Hemoglobin (Hgb)	$> 9.0$ g/dL (with or without transfusion)
Renal	
Serum Creatinine	$\leq 2 \times \text{ULN}$
Hepatic	

Bilirubin 	$\leq 1.5 \times$ upper limit of normal (ULN)
Aspartate aminotransferase (AST)	$\leq 3 \times$ ULN
Alanine aminotransferase (ALT)	$\leq 3 \times$ ULN

Except subjects with Gilbert Syndrome, who can have total bilirubin  $< 3.0$  mg/dL

9. Baseline testosterone  $\geq 100$  ng/dL
10. Recovery from acute toxicity related to prior therapy, including surgery and radiation, or no treatment-related toxicity  $\geq$  grade 2.
11. History of prior malignancy or concurrent separate malignancy is not an exclusion criterion so long as the non-prostate malignancy is stable and does not require any treatment.
12. Able to understand and sign informed consent and adhere to study procedures.
13. Male patients whose female partners are of reproductive potential must agree to use a contraception during the trial period.

### 3.2. Exclusion Criteria

Eligible patients must not have any of the following exclusion criteria:

1. Current use of ADT or plan to initiate ADT during trial period
2. Major surgery or radiation therapy within 14 days of starting study treatment
3. Subjects with active autoimmune disease. Patients with a history of autoimmune disease that has not required systemic immunosuppressive therapy or does not threaten vital organ function including central nervous system, heart, lungs, kidneys, skin, and gastrointestinal tract will be allowed.
4. Known history of immune deficiencies or chronic viral infections including HIV, HBV, and HCV (patients with prior therapy for HBV or HCV is permitted if viral clearance was documented).
5. Concurrent medical condition requiring use of systemic corticosteroids with prednisone  $>10$  mg per day or equivalent. Use of inhaled, nasal, and topical steroids (applied to small body areas) is allowed.
6. Current use (within past 4 weeks) of other prohibited medications including anti-cancer therapies, hormonal therapies, 5-alpha reductase inhibitors, and alternative medications known to alter PSA (e.g. phytoestrogens and saw palmetto).
7. Prior treatment with immune checkpoint inhibitors. (Prior cancer vaccines are allowed.)
8. Serious intercurrent medical or psychiatric illness that, in the judgment of the investigator, would interfere with patient's ability to carry out the treatment program.

## 4. SUBJECT REGISTRATION

### 4.1. General Guidelines for DF/HCC Institutions

Institutions will register eligible participants in the Clinical Trials Management System (CTMS) OnCore. Registrations must occur prior to the initiation of any protocol-specific therapy or intervention. Any participant not registered to the protocol before protocol-

specific therapy or intervention begins will be considered ineligible and registration will be denied.

An investigator will confirm eligibility criteria and a member of the study team will complete the protocol-specific eligibility checklist.

Following registration, participants may begin protocol-specific therapy and/or intervention. Issues that would cause treatment delays should be discussed with the Overall Principal Investigator (PI). If the subject does not receive protocol therapy following registration, the subject must be taken off-study in the CTMS (OnCore) with an appropriate date and reason entered.

Applicable DF/HCC policy (REGIST-101) must be followed.

